## 1 PROTOCOL SUMMARY

### 1.1 SYNOPSIS

|   |  |
|---|--|
| Title:                             | Virtual Reality by Mobile Phone: Improving Child Pedestrian Safety   |
| Study Background:                  | Pedestrian injury is a serious public health concern for children in the United States and around the world. We have previously studied virtual reality as a mechanism to train children to be safer pedestrians. Virtual reality offers the opportunity for repeated practice at the complex cognitive-perceptual task of crossing a street, and we have demonstrated that it is effective to help 7- and 8-year-old children learn to cross streets more safely.   |
| Objectives:                        | This protocol extends previous work in two ways. First, we are unsure how much practice and training children need to achieve adult levels of pedestrian safety. We will offer children in this study up to 25 sessions of practice crossing the street in a virtual world to see when they achieve adult levels of safety. Second, we will evaluate whether training using a virtual reality program delivered to a mobile smartphone platform is as effective as training in a larger semi-immersive virtual pedestrian environment we have used previously. |
| Study Population:                  | 7 and 8 year old children  |
| Phase:                             | III  |
| Description of Study Intervention: | Pedestrian safety training in virtual reality  |

## 2 INTRODUCTION

### 2.1 STUDY RATIONALE

Pedestrian injury is a serious public health risk for children in the United States and worldwide. One way to reduce pedestrian injury risk is by training children to cross streets more safely. Previous research indicates virtual reality may be an ethical and safe way to provide such training, and this trial was designed to further evaluate virtual reality as a means to teach children pedestrian street-crossing skills.

### 2.2 BACKGROUND

We have conducted two clinical trials evaluating whether training in a virtual reality environment helps children learn to cross the street more safely. In the first, 240 children were randomly assigned to one of four conditions. Children trained in the virtual reality environment achieved levels of pedestrian safety that were approximately equivalent to children trained individually at streetside locations. They performed better than children trained using websites and videos, and better than children in a no-contact control group.

In the second trial, we evaluated whether training in a virtual reality environment placed in community settings (schools or YMCAs) was effective. We found children did learn to be safer pedestrians through that training, although they did not achieve levels of safety as much as children in the previous study. One reason for this may be that children in this second trial were exposed to six 15-minute training sessions whereas children in the first trial were exposed to six 30-minute training sessions, or double the amount.

We have conducted previous work demonstrating the Google Cardboard platform delivering virtual reality to children by mobile phone is usable, feasible, and safe. Other laboratories also use virtual reality for evaluation of children's pedestrian, bicycling, and other behaviors.

### 2.3 RISK/BENEFIT ASSESSMENT

#### 2.3.1 KNOWN POTENTIAL RISKS

Physical risk includes (a) minor risk of motion sickness while engaging in a virtual environment, (b) risk of injury from moving traffic while completing the "shout" and "two-step" assessments at streetside locations off the road but near moving traffic, and (c) slight chance of iatrogenic risks, whereby children or parents take greater risk following participation in training because they think the children are safer.

Psychological risks include (a) embarrassment from being videotaped or engaging in the research protocol, and (b) embarrassment for parents to answer questionnaires that are mildly invasive.

Social risks. We believe there is minimal social risk from participating in this study. The primary risk results from the possibility for a breach of confidentiality. No data we collect will be highly personal, but we will collect information that participants may wish to keep private (such as household income), and the risk of a confidentiality breach is a social risk.

There are no anticipated economic or legal risks.

### 2.3.2 KNOWN POTENTIAL BENEFITS

It is now known, which is why we are conducting this research, but children may learn to be safer pedestrians through participation in this study.

## 3 STUDY DESIGN

### 3.1 OVERALL DESIGN

A non-inferiority randomized controlled trial will be conducted.

## 4 STUDY POPULATION

### 4.1 INCLUSION CRITERIA

- Child age 7 or 8 years

### 4.2 EXCLUSION CRITERIA

- Inability of child or parent to communicate in English
- Previous participation of a sibling in the study
- Physical or mental disability that prohibits child from valid participation in the study

## 5 STUDY INTERVENTION

### 5.1 STUDY INTERVENTION(S) ADMINISTRATION

#### 5.1.1 STUDY INTERVENTION DESCRIPTION

##### Virtual Reality Platforms

Two virtual reality (VR) platforms will be used, the “kiosk” VR in a laboratory setting and the smartphone-based VR delivered via smartphone. In the kiosk system, children stand on a plywood curb and step down onto a pressure plate to trigger the system for crossing. The system runs on a single Windows 7 PC with an Intel Core i5-3330 3.0GHz Quad-Core desktop processor and GeForce GT 640 video card. The virtual environment is displayed on 3 vertically mounted Samsung MD55C 55” Direct-lit LED displays and is moved vertically on the displays to match the participant’s eye-level. In the smartphone system, children use a standard Android mobile smartphone inserted into a durable View-Master® VR viewer. The street-crossing simulator software on both systems are built on top of the Unity game engine with identical virtual environments, game play logic and data collection.

In both VR platforms, prior to children entering the VR, the researcher enters a walking speed (based either on the child's previously-measured walking speed in a separate location or age-based averages), gender, and skin tone (to select sex- and race-matched avatar). Children view a bi-directional roadway modeled after an actual street environment near a local school. Traffic density, traffic speed, and vehicle types are adjusted to researcher preferences and child skill level. Ambient and Doppler-accurate traffic noise are delivered. Over a dozen types of vehicles (including cars, SUVs, pick-ups, and also ambulances, school buses, etc.) appear in random order at researcher-determined frequencies. When children deem it safe, they step off the simulated curb to trigger a pressure plate (semi-immersion) or push a button (smartphone). In the kiosk VR, the virtual world view then changes from first to third-person, permitting children to view themselves crossing. This switch from first to third person happens seamlessly and most users do not even notice the switch when asked about it later. In the smartphone VR, the virtual world remains at first-person view, as the viewpoint follows the avatar across the street.

Following the avatar's crossing, the child is informed about the safety of crossing.

### Training Protocol

Children will complete up to 25 training sessions. Training sessions will be scheduled about twice a week and will be identical in both groups except for the VR platform used. Children will engage in the VR for 3 sets of 15 crossings, or 45 crossings at each training session (expected duration ~30 minutes). The first two sets of crossings will be tailored to children's ability level, with traffic density set just beyond the level they previously succeeded crossing at. The third set of crossings will be standardized for all visits, at 30 MPH and 10 vehicles/minute/lane. Along with serving as a training trial, this third set will typically be a little easier for children, providing positive feedback and motivation for training. It also will offer a standardized assessment of ability.

All children will complete six visits to the laboratory for training. Following the sixth and all subsequent visits, we will monitor each child's number of unsafe crossings in the final standardized assessment.

When children complete two consecutive visits at a level equal to or safer than the average adult performance, they will be considered "competent" pedestrians functioning like an adult and training will be discontinued. Adult performance will be defined based on previous research with >300 adults.

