Specific Aim 2 is to (2a) demonstrate that most children achieve adult-level pedestrian functioning after 25 training sessions and (2b) demonstrate how many training sessions are sufficient to achieve this functioning. Because the safety of crossings is ultimately of greatest interest from a public health perspective, unsafe crossings will serve as the primary outcome for this aim; start delay will serve as a critical secondary outcome. Adult functioning will be estimated based on the performance of 311 healthy adults in four previous studies. Aim 2a will be evaluated via simple descriptive statistics to determine what percent of children achieve an unsafe crossings rate equivalent to adults in multiple simulated crossings. Aim 2b will also be evaluated descriptively, in this case by examining the average number of trials needed to achieve adult functioning across the sample, as well as the trajectory and distribution of that variable.

Specific Aim 3 is to test whether training in the smartphone VR improves children's street-crossing skills after 25 training trials, or fewer if adult functioning is achieved earlier, at a rate not inferior to improvement seen in the semi-immersive kiosk VR. Two dependent variables will be primary, start delay and unsafe crossings (other measures will be considered secondarily) and we will test the aim with the same hypothesis, analyses, and assumptions as in Specific Aim 1. Two sets of analyses will be conducted, one to test change from baseline to post-intervention and the second to test change from baseline to follow-up visits 6 months later.

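### The only written competence rule starts at visit 6, so an Aim 2b session count built on it has a floor of 6 or 7; separately, Aim 2a has no baseline reference

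*Combined protocol and SAP*

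**What the plan says.** All references are to the combined protocol and SAP.

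- **Minimum and maximum (5.1.1, Training Protocol).** "All children will complete six visits to the laboratory for training", and "Children will complete up to 25 training sessions".
- **Start of monitoring (same section).** "Following the sixth and all subsequent visits, we will monitor each child's number of unsafe crossings in the final standardized assessment".
- **Competence rule (same section).** "When children complete two consecutive visits at a level equal to or safer than the average adult performance", they are classed as competent and training ends.
- **Data at each visit (same section).** "Children will engage in the VR for 3 sets of 15 crossings, or 45 crossings at each training session". "The third set of crossings will be standardized for all visits, at 30 MPH and 10 vehicles/minute/lane", and this set is also described as an assessment of ability.
- **Aim 2 (8.3).** Aim 2a is the percentage of children whose unsafe-crossing rate is equivalent to that of adults over multiple simulated crossings. Aim 2b is to be answered by "examining the average number of trials needed to achieve adult functioning across the sample, as well as the trajectory and distribution of that variable". Both are descriptive. The adult level comes from 311 adults in earlier studies; the rate itself is not given.
- **Eligibility (4.1, 4.2).** The one inclusion criterion is "Child age 7 or 8 years". The exclusions concern language, a sibling's earlier participation, and disability.
- **Baseline (5.2, 8.3).** Baseline data are collected before the randomization draw, and the Aim 1 and Aim 3 analyses use baseline values.

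**The concern.** The synopsis says the sponsor does not know how much practice children need, and Aim 2b is the part of the plan that answers this. If the count can begin only at the sixth or seventh session, a child at adult level from the first visit and a child who gets there at visit 6 receive the same value. The lower end of the distribution, which shows how short a training programme could be, collapses to a single point, and the mean moves up.

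Aim 2a has a different weakness. Both arms are trained, entry is not restricted by crossing ability, and no percentage at adult level before training is planned. The reported percentage therefore mixes children trained to adult level with children who arrived there.

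**Working it through.** **1. No planned figure to reproduce.** The documents state no expected percentage or session count for Aim 2. The sample-size figures in 8.2 concern Aims 1 and 3 and do not bear on this point.

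**2. The floor, by counting.** Take the session count as the visit at which the two-visit rule is met, that is, the second of the pair.

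| Earliest eligible pair | Smallest possible count |
|---|---|
| Visits 6 and 7 (both within the monitored period) | 7 |
| Visits 5 and 6 (visit 5 may open the pair) | 6 |
| Visits 1 and 2 (same rule from the first visit) | 2 |

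If the first visit of the pair were counted, each value would drop by one. The plan does not say which is meant.

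**3. Whether the floor is forced by the data.** It is not. The standardized set is run at every visit, so visits 1 to 5 supply the same 15-crossing measure as later visits. The floor arises only if the stop rule is also the analysis definition.

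**4. Size, as illustration only.** The adult rate, the children's baseline rate and the learning curve are not in the documents. Assumptions:

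- The true unsafe rate at session 6, p₆, is Beta with mean 0.20 and SD 0.15 or 0.20. Section 8.2 gives mean 0.20 and SD 0.20 at follow-up in an earlier study.
- logit p_v = logit p₆ − (g/6)(v − 6), with g = 0.4, 0.8 or 1.2. This implies baseline means of about 0.25 to 0.40.
- The adult average is 5%, 10% or 15%. Since 15 × 0.05 = 0.75, 15 × 0.10 = 1.5 and 15 × 0.15 = 2.25, a set passes with at most 0, 1 or 2 unsafe crossings.

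This makes 2 × 3 × 3 = 18 settings, each with 100,000 simulated children and 25 visits:

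| Quantity | Range |
|---|---|
| Children recorded at exactly 7 (floor 7) | 10–50% |
| Of those, already met the two-visit rule by visit 5 | 53–92% |
| All children meeting the rule by visit 5 | 10–55% |
| Excess of mean count among achievers, floor 7 against count from visit 1 | 0.6–3.3 sessions |
| The same, floor 6 | roughly 0.5–2.6 sessions |
| Change in percentage ever reaching the criterion | at most about 0.2 points |

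A second model starts from a mean rate of 0.30 (SD 0.20) at visit 1. It gives the mean count among achievers, with the percentage reaching the criterion in brackets:

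| Learning per session (logit); pass mark | From visit 1 | Floor 6 | Floor 7 |
|---|---|---|---|
| 0.10; ≤2 of 15 | 8.63 (94.9%) | 10.41 (94.9%) | 10.93 (94.9%) |
| 0.05; ≤1 of 15 | 10.04 (62.7%) | 11.98 (62.6%) | 12.53 (62.5%) |
| none; ≤2 of 15 | 5.45 (51.4%) | 8.97 (50.1%) | 9.83 (49.7%) |

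With learning, the excess is 1.8 to 2.5 sessions (10.41 − 8.63 = 1.78; 12.53 − 10.04 = 2.49). With no learning at all, an extreme case, it is 3.5 to 4.4 (8.97 − 5.45 = 3.52; 9.83 − 5.45 = 4.38).

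**5. What this says about Aim 2a.** The start of monitoring hardly moves the percentage: at most about 0.2 points in the 18 settings, and 51.4 − 49.7 = 1.7 points in the no-learning case. The weakness of Aim 2a comes from the missing baseline reference. The no-learning row shows why that matters: about half the children reach the criterion although training did nothing.

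**6. Chance passes.** For a child with a true unsafe rate of 0.20 and a pass mark of 1 of 15, one set is passed with probability 0.8¹⁵ + 15 × 0.2 × 0.8¹⁴ = 0.035 + 0.132 = 0.167. A given pair of visits is passed with probability 0.167² = 0.028. Each extra eligible pair adds such an opportunity.

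**The case against.** **The monitoring sentence governs when training stops, not how Aim 2b is computed.** This stands. A reader might infer that Aim 2b cannot return fewer than six or seven sessions, or that data from visits 1 to 5 are discarded. The documents say neither: 8.3 does not refer to the stop rule, and the standardized set is available from the first visit. What remains is that no other visit-level definition is written, so an analyst either inherits the floor or has to choose a definition later.

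**The six-session minimum has a purpose.** This also stands. Aim 1 compares the arms after six training trials, so every child needs them. Nothing here argues for changing it.

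**Late monitoring does not inflate Aim 2a.** Correct, as step 5 shows. A reader might link the two; the figures do not support that.

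**Aim 2a is descriptive and makes no causal claim.** Fair. Even so, a percentage said to be achieved after training will be read as a result of training, and a baseline figure lets the reader judge that.

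**The magnitudes are assumed.** True. With mean and SD both 0.20 the distribution is Beta(0.6, 2.4), which piles up near zero and favours early passes. Nor is visit 1 an untrained baseline: its third set follows 30 crossings with feedback, and that of visit 2 follows 45 + 30 = 75.

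**Counting from visit 1 is noisy too.** In the 18 settings, 7 to 30% of children passing by visit 5 were not truly at adult level by then. In one coding of the least favourable setting (SD 0.15, slowest learning, adult average 5%) the means were 12.6 floored, 11.9 true and 10.3 from visit 1, so the count from visit 1 was further off. Overall, however, the floored mean exceeded the true crossing session in every setting, and the count from visit 1 was closer to it in at least 16 of 18.

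**Conclusion.** The point holds in conditional form. If Aim 2b takes over the stop rule, its session count has a floor of 7, or 6 if visit 5 may open the pair, counting the second visit. The floor itself follows from the text alone. The upward bias in the mean has a clear direction but no size that the documents can settle: roughly 0.5 to 3 sessions among achievers under the learning curves assumed above, and more if children do not learn at all.

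Independently of this, the Aim 2a percentage cannot separate children trained to adult level from those already there. The documents do not show how many children are at adult level at entry or after a few sessions, so no claim is made that there are many.

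The non-inferiority tests in Aims 1 and 3 are not affected. The change is worth making because it bears directly on a stated aim and costs little.

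**What to change.** Keep the six-session minimum and the training stop rule as written. In section 8.3:

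1. **Aim 2b.** Derive the session count by applying the same two-consecutive-visit criterion to the standardized third set from visit 1. State which visit of the pair is the count. Report the count under the stop rule alongside, marked as left-censored at 6 or 7, and say whether visit 5 may open the pair.
2. **Aim 2a.** Report the percentage at adult level at the pre-randomization baseline VR assessment, and the percentage reaching adult level among children not at that level at baseline. Visit 1 should not stand in for baseline. The documents do not say whether the baseline assessment uses the traffic settings of the third set. The plan should state this, since the comparison with the adult rate depends on it.
3. **Chance passes.** Note that with 15 crossings per set some early passes will be chance, and interpret the earliest counts accordingly.

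Cost: SAP wording and a little more analysis of data already planned, with no new visit and no change to training. The Aim 2a denominator for the second percentage is smaller, and the headline may look less favourable.

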## 5.2 MEASURES TO MINIMIZE BIAS: RANDOMIZATION

Random assignment to the condition in which the child received training will be conducted using simple randomization by asking children to draw a slip of paper from a large envelope at the end of baseline data collection.

## 6 STUDY INTERVENTION DISCONTINUATION AND PARTICIPANT DISCONTINUATION/WITHDRAWAL

### 6.1 DISCONTINUATION OF STUDY INTERVENTION

Training will be discontinued after 25 sessions if children have not yet reached adult competency at that point. Training will be discontinued also if there is any sign of adverse or iatrogenic effect.

### 6.2 PARTICIPANT DISCONTINUATION/WITHDRAWAL FROM THE STUDY

Participants are free to withdraw from participation in the study at any time upon request. An investigator may discontinue or withdraw a participant from the study for the following reasons:

- Non-compliance to study protocol
- If any clinical adverse event (AE), laboratory abnormality, or other medical condition or situation occurs such that continued participation in the study would not be in the best interest of the participant

### 6.3 LOST TO FOLLOW-UP

A participant will be considered lost to follow-up if they fail to attend multiple scheduled visits and/or are unable to be contacted by the study site staff.

## 7 STUDY ASSESSMENTS AND PROCEDURES

### 7.1 STUDY ASSESSMENTS

In all pedestrian simulations (both virtual and streetside), several measures will be collected. Unsafe crossings will be the primary outcome, defined as the sum of “hits” with simulated vehicles, plus “close call” instances when the child was within one second of being hit by an oncoming vehicle. We also will assess several secondary measures, including start delay (temporal lapse between a safe gap between vehicles emerging and children entering that gap to cross the street), time to contact (shortest distance between children and an oncoming virtual vehicle), attention to traffic (looks left and right divided by wait time), missed opportunities (rejected gaps  $\geq$  1.5 times participant’s crossing time), wait time (average time waiting to cross, divided by cars that pass while waiting), and gap size (temporal gap crossed within).

We will collect other measures as potential covariates. Parents will report basic demographic data (e.g., child gender, race/ethnicity, birthdate; family SES), child temperament, and children’s pedestrian behavior and habits. Children will complete a screener of verbal intelligence.

### 7.2 ADVERSE EVENTS AND SERIOUS ADVERSE EVENTS

#### 7.2.1 DEFINITION OF ADVERSE EVENTS (AE)

Adverse event means any untoward medical occurrence associated with the use of an intervention in humans, whether or not considered intervention-related (21 CFR 312.32 (a)).

#### 7.2.2 DEFINITION OF SERIOUS ADVERSE EVENTS (SAE)

An adverse event (AE) is considered “serious” if, in the view of either the investigator or sponsor, it results in any of the following outcomes:

- Death
- A life-threatening adverse event (of note, the term “life-threatening” refers to an event in which the participant was at risk of death at the time of the event, rather than to an event which hypothetically might have caused death if it were more severe)
- inpatient hospitalization or prolongation of existing hospitalization

- a persistent or significant incapacity or substantial disruption of the ability to conduct normal life functions
- or a congenital anomaly/birth defect.

Important medical events that may not result in death, be life-threatening, or require hospitalization may be considered serious when, based upon appropriate medical judgment, they may jeopardize the participant and may require medical or surgical intervention to prevent one of the outcomes listed in this definition. Examples of such medical events include allergic bronchospasm requiring intensive treatment in an emergency room or at home, blood dyscrasias or convulsions that do not result in inpatient hospitalization, or the development of drug dependency or drug abuse.

---

